5.6.4. Vital Signs

Participants with markedly abnormal vital signs will be listed.

Table 3: Markedly Abnormal Vital Signs

Vital Sign	Criteria
Pulse	>[120] bpm and with >[30] bpm increase from baseline
	<[50] bpm and with >[20] bpm decrease from baseline
Systolic blood pressure	>[180] mm Hg and with >[40] mm Hg increase from baseline
	<[90] mm Hg and with >[30] mm Hg decrease from baseline
Diastolic blood pressure	>[105] mm Hg and with >[30] mm Hg increase from baseline
	<[50] mm Hg and with >[20] mm Hg decrease from baseline
Temperature	>[38]°C and with >=[1]°C increase from baseline
Respiratory rate	>[20] breaths per minute

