6. STUDY INTERVENTION AND CONCOMITANT THERAPY

6.1. Study Intervention Administered

Study intervention administration must be captured in the source documents and the electronic case report form (eCRF).

Bermekimab will be manufactured and provided under the responsibility of the sponsor. Refer to the [IB](#) for a list of excipients.

For details on rescue medications, refer to Section [6.8.4](#), Rescue Medication. For a definition of study intervention overdose, refer to Section [6.7](#), Treatment of Overdose.

Approximately 10 participants are planned to receive weekly 800 mg of IV bermekimab or placebo in Part A. Approximately 30 participants are planned to receive weekly 1200 mg of IV bermekimab or placebo in Part B. After the initial 10 participants (8A:2P) have completed 6 weeks of dosing in Part B, safety, PK, PD, and efficacy will be analyzed to determine an appropriate dose to be used in Part C. Approximately 20 participants are planned to receive the determined dose of bermekimab and placebo. The maximum dose to be considered for Part C will be 2400 mg IV weekly ([Table 2](#)).

Table 2: Description of Interventions

Part Name	Part A	Part B	Part C	N/A
Intervention Name	bermekimab	bermekimab	bermekimab	Placebo
Dose Formulation	sterile liquid formulation of 350 mg (175 mg/mL) of bermekimab in a prefilled syringe (PFS) with an injectable volume of 2.0 mL.	sterile liquid formulation of 350 mg (175 mg/mL) of bermekimab in a PFS with an injectable volume of 2.0 mL.	sterile liquid formulation of 350 mg (175 mg/mL) of bermekimab in PFS with an injectable volume of 2.0 mL.	Saline vials
Unit Dose Strength(s)	175 mg/mL	175 mg/mL	175 mg/mL	N/A
Dosage Level(s)	800 mg intravenous (IV) infusion weekly from Week 0 through Week 15	1200 mg IV infusion weekly from Week 0 through Week 15	TBD mg IV infusion weekly from Week 0 through Week 15	IV infusion weekly from Week 0 through Week 15
Route of Administration	IV infusion	IV Infusion	IV Infusion	IV Infusion
Use	Experimental	Experimental	Experimental	Placebo comparator
Investigational Medicinal Product	Yes	Yes	Yes	No
Non-Investigational Medicinal Product /Auxiliary Medicinal Product	No	No	No	No
Sourcing	Provided centrally by the sponsor			

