8.2.2. Vital Signs

Temperature, pulse/heart rate, respiratory rate, blood pressure will be obtained prior to study intervention administration at visits specified in the schedule of activities.

In addition, all participants will have an extended in-clinic observation period of approximately 4 hours during the first 2 infusions. In this period, vital signs will be taken at the following time points: 0 hour (start of infusion), 30 minutes, 1 hour, 1 hour and 30 mins, 2 hours (end of infusion), 2 hours and 30 mins, 3 hours, 3 hours and 30 mins, and 4 hours (post-infusion). Beyond the first 2 infusions, all participants will have approximately a 1 hour infusion period and at least a 1 hour observation post infusion, as well as vital signs taken every 30 minutes.

Blood pressure and pulse/heart rate measurements should be preceded by approximately 5 minutes of rest in a quiet setting without distractions (eg, television, cell phones).

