5. STATISTICAL ANALYSES

5.1. General Considerations

The statistical analyses will include all analyses from Week 0 through Week 20 (the final safety follow-up).

In general, baseline is defined as the last observation prior to or at the time of the first study agent administration, unless otherwise specified.

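### For infusions 2–16, SAP Table 3 judges vital-sign change only against the Week 0 baseline, so some acute in-infusion changes that cross an absolute limit can go unlisted

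*SAP*

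**What the plan says.** SAP 5.6.4 states: "Participants with markedly abnormal vital signs will be listed". Table 3 sets the criteria. The pulse, systolic and diastolic rows, and the temperature row, each combine an absolute limit with a change condition. Examples are ">[120] bpm and with >[30] bpm increase from baseline" for high pulse and "<[90] mm Hg and with >[30] mm Hg decrease from baseline" for low systolic pressure. Respiratory rate has a limit only: ">[20] breaths per minute".

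The reference for change comes from SAP 5.1: "In general, baseline is defined as the last observation prior to or at the time of the first study agent administration, unless otherwise specified". SAP 5.6.4 specifies nothing different, so every change in Table 3 is measured from one Week 0 value per participant. SAP 5.6.4 also does not say which readings the listing covers.

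On data collection, Protocol 8.2.2 says vital signs "will be obtained prior to study intervention administration at visits specified in the schedule of activities". It adds serial readings every 30 minutes through infusion and observation. Footnotes s and v of the Schedule of Activities (Protocol 1.3) give 0 to 4 hours for the first two infusions and 0 to 2 hours for later ones. Table 2 of Protocol 6.1 has dosing at Weeks 0 to 15, for instance "800 mg intravenous (IV) infusion weekly from Week 0 through Week 15".

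**The concern.** The serial readings are there to show what happens during and shortly after an infusion. The natural reference for such a change is the reading taken just before that infusion. It is collected, but Table 3 does not use it. At later visits the change condition mixes the acute effect with whatever drift has occurred since Week 0, up to 15 weeks earlier. If the drift runs against the acute change, a reading beyond the absolute limit can fail the change condition.

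Clinically significant vital-sign abnormalities are a secondary safety endpoint in both documents, and infusion-related reactions are a named risk in Protocol 2.3. Protocol 9.4.4 planned descriptive summaries of vital signs over time. After early termination the SAP provides listings only (SAP 1 and Appendix 2), and Table 3 is the only vital-sign listing. A reading that fails Table 3 appears in no other planned vital-sign output.

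**Working it through.** The plan gives no figure on this point to reproduce. The check has four steps.

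**1. Readings the choice of reference can affect.** Weeks 0–15 give 16 infusions. Infusions 1 and 2 have 9 readings each (0 to 4 h, every 30 min), of which 8 fall after the start. Infusions 3–16 have 5 each (0 to 2 h), of which 4 fall after the start.
- Post-start readings: 2 × 8 + 14 × 4 = 72.
- At infusion 1 (8 readings), baseline is itself the same-visit pre-infusion value, so nothing changes.
- Readings that can be affected: 72 − 8 = 64, or 89%.

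Footnote v refers to infusions 3 through 15, one short of the 16-infusion schedule. Read literally, the counts are 68 and 60. The two passages need reconciling.

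**2. When the reference matters.** Let A be the absolute limit and C the required change. Once A is crossed, the change condition is met automatically if the reference is ≤ A − C (high rows) or ≥ A + C (low rows).

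| Row | A | C | Automatic if reference is |
|---|---|---|---|
| Pulse high | 120 | 30 | ≤ 90 |
| Pulse low | 50 | 20 | ≥ 70 |
| Systolic high | 180 | 40 | ≤ 140 |
| Systolic low | 90 | 30 | ≥ 120 |
| Diastolic high | 105 | 30 | ≤ 75 |
| Diastolic low | 50 | 20 | ≥ 70 |
| Temperature | 38 °C | 1 °C | ≤ 37 °C |

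A value beyond the limit can be missed only if the Week 0 reading lies on the other side, for example systolic below 120 or pulse above 90.

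**3. Worked cases.**

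| Case | Week 0 | Pre-infusion | During | Change from Week 0 | Change within visit | Listed on Week 0 | Listed on same visit |
|---|---|---|---|---|---|---|---|
| Systolic | 112 | 128 | 86 | −26 | −42 | No | Yes |
| Pulse | 96 | 74 | 124 | +28 | +50 | No | Yes |
| Pulse | 80 | 100 | 124 | +44 | +24 | Yes | No |

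**4. Illustrative frequency, on assumed values.** Each person has a true mean. The Week 0 and pre-infusion readings each vary around it with a visit-to-visit SD. The in-infusion reading equals the pre-infusion reading plus a fixed change. The miss rate is the share of participants meeting the criterion on the same-visit reference who fail it on Week 0.

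| Change | Assumed mean; between-person SD | Visit SD | Missed |
|---|---|---|---|
| Systolic fall 35 | 122; 12 | 4, 7, 10 | 15%, 22%, 24% |
| Systolic fall 45 | 122; 12 | 4, 7, 10 | 0.3%, 5%, 10% |
| Pulse rise 35 | 75; 10 | 6, 8, 10 | 12%, 13%, 13% |
| Pulse rise 40 | 75; 10 | 6, 8, 10 | 5%, 7%, 9% |
| Pulse rise 50 | 75; 10 | 6, 8, 10 | 0.4%, 2%, 3% |

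Adding reading noise of SD 5 lowers the 35 mm Hg systolic figures to 12%, 18% and 21%. Varying the pulse mean over 75–80 and the between-person SD over 8–12 gives 9–19% at a rise of 35, 4–13% at 40 and 0–4% at 50. At a visit SD of 4, the 40 bpm figure is about 2% (mean 75, SD 10).

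**The case against.** The strongest reply is that nothing here is an error. A fixed baseline follows SAP 5.1, and the protocol's own infusion-hypotension rule (Protocol 7.1) also refers to a participant's baseline value. Table 3 is about markedly abnormal values and does not claim to detect infusion reactions. Those are an adverse-event endpoint. Protocol 8.2 requires clinically relevant changes to be recorded as adverse events, SAP 5.6.2 lists treatment-emergent events, and the data review committee sees unblinded safety data. With few participants and no formal analysis, little turns on one listing.

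Most of this stands. It limits the consequence but does not close the gap, because vital-sign abnormalities are a safety endpoint in their own right. It also rules out four stronger inferences a reader might draw:

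- **That all 16 infusions are affected.** At infusion 1 the two references coincide.
- **That participants are falsely listed.** Every listed value has crossed an absolute limit and changed from baseline as defined. In the third worked case the listing is correct, even though the in-infusion rise is only 24 bpm.
- **That infusion reactions drop out of the safety data.** They are captured as adverse events whatever Table 3 shows.
- **That about a third of pulse events are missed.** Treating Week 0 minus pre-infusion pulse as normal with mean 0 and variance 2 × SD² gives 28–36% at a 35 bpm rise and 12–24% at 40, for SD 6–10. That ignores the limit of 120. Exceeding it after a 35 bpm rise needs a pre-infusion pulse above 85. Such readings tend to sit above the person's own mean, so Week 0 tends to be lower and a miss less likely.

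**Conclusion.** The point holds as a gap in sensitivity, not as a contradiction between the documents. For infusions 2–16, the rule as written can leave unlisted an acute change in pulse, blood pressure or temperature that crosses an absolute limit. At most 64 of 72 scheduled post-start readings per participant are exposed, and only where the Week 0 value lies on the restrictive side of the thresholds above. That these readings fall within Table 3 is itself inferred, since SAP 5.6.4 names no time points.

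The worked cases need no assumption beyond the Table 3 rule. The percentages do: the means, SDs and sizes of change are all assumed, and the miss rate falls quickly as the acute change grows. Low systolic pressure is the stronger example. Respiratory rate, adverse-event reporting and every efficacy conclusion are unaffected. The change is worth making because it is cheap and individual readings are all that will be reported.

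**What to change.** In SAP 5.6.4:

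- State that Table 3 applies to readings taken during infusion and during post-infusion observation, as well as to the other scheduled readings.
- Keep the Week 0 criterion unchanged.
- Add wording to this effect: for infusions 2–16, change is also computed from the last reading before that visit's infusion begins; a participant is listed if Table 3 is met on either reference, and both changes are shown.

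This removes no one from the listing. It needs one or two sentences and one derived variable from data already collected. The downside is a slightly longer listing, in which some rows meet only one of the two references.

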5.7. Other Analyses

5.7.1. Pharmacokinetics and Immunogenicity (Antibodies to Bemeckimab)

Due to early termination of the study by the sponsor with a small number of participants enrolled, pharmacokinetics and immunogenicity analyses will not be performed.

6. SUPPORTING DOCUMENTATION

6.1. Appendix 1 List of Abbreviations

AD	Atopic dermatitis
ADIS	Atopic Dermatitis Itch Scale
AE	Adverse event
ALT	alanine aminotransferase
AST	aspartate aminotransferase
ATC	anatomic and therapeutic class
AUC	area under the curve
BMI	body mass index
BSA	body surface area
CI	confidence interval
Cmax	maximum concentration
CRF	case report form
CSR	Clinical Study Report
CTCAE	Common Terminology Criteria for Adverse Events
CV	coefficient of variation
DRC	Data Review Committee
DPS	Data Presentation Specifications
EASI	Eczema Area and Severity Index
eCRF	electronic case report form
FAS	full analysis set
FDA	Food and Drug Administration
ICH	International Conference on Harmonisation
IGA	Investigator Global Assessment
IQ	interquartile
IWRS	interbermekimab web response system
LLOQ	lower limit of quantification
MedDRA	Medical Dictionary for Regulatory Activities
NRS	Numeric Rating Scale
PD	pharmacodynamic(s)
PGIS	Patient Global Impression of Severity
PI	principal investigator
PK	pharmacokinetic(s)
POEM	Patient-oriented eczema measure
PP	per protocol
PROMIS	Patient-reported outcomes measurement information system
SAE	serious adverse event
SAP	Statistical Analysis Plan
SD	standard deviation
TEAE	treatment-emergent adverse event
vIGA-AD	Validated Investigator Global Assessment for Atopic Dermatitis
WHO	World Health Organization

6.2. Appendix 2 Changes to Protocol-Planned Analyses

Due to early termination of the study with a small number of participants enrolled, only data listings will be provided. No formal analyses will be performed.

6.3. Appendix 3 Demographics and Baseline Characteristics

The demographic (age, weight, height, BMI, race, sex, and ethnicity) and baseline disease characteristics (duration of AD disease, EASI score, vIGA-AD, hand dermatitis IGA, GISS, POEM, ADIS, SCORAD score, BSA, NRS pain, NRS Itch, DLQI, PROMIS-29, PGIS) will be listed.

6.4. Appendix 4 Protocol Deviations

Major protocol deviations will be listed by following category.

- Developed withdrawal criteria but not withdrawn
- Entered but did not satisfy criteria
- Received a disallowed concomitant treatment
- Received wrong treatment or incorrect dose
- Other

6.5. Appendix 5 Prior and Concomitant Medications

Prior medications are defined as any therapy used before the day of first dose (partial or complete) of study intervention. Previous atopic dermatitis medications/therapy will be listed by intervention group.

Concomitant medications will be coded using the World Health Organization Drug Dictionary (WHO-DD). Concomitant medications are defined as any therapy used on or after the same day as the first dose of study intervention, including those that started before and continue on after the first dose of study intervention.

A listing of concomitant medications will be provided.

6.6. Appendix 6 Medical History

Medical history will be listed by intervention groups.

6.7. Appendix 7 Intervention Compliance

A listing of study intervention administration will be provided.

6.8. Appendix 8 Adverse Events of Special Interest

Not applicable.

6.9. Appendix 9 Medications of Special Interest

Not applicable.

6.10. Appendix 10 Laboratory Toxicity Grading

The grading scale use for lab assessments is based on ‘Common Terminology Criteria for Adverse Events (CTCAE)’.

If a laboratory value falls within the grading as specified below but also within the local laboratory normal limits, the value is considered to be normal and will be reset to grade 0.

Pre-baseline measurements will use the same grading ranges as applied to baseline measurements. In case a test has two sets of ranges – one for baseline normal and one for baseline abnormal, the one for baseline normal will be applied for all measurements taken pre-baseline and on baseline.

Participants with toxicity grades ≥ 2 will be listed.

CTCAE Term	Grade 1	Grade 2	Grade 3	Grade 4	Janssen implementation notes
Blood and lymphatic system disorders					
Anemia	Hemoglobin (Hgb) <LLN - 10.0 g/dL; <LLN - 6.2 mmol/L; <LLN - 100 g/L	Hemoglobin (Hgb) <10.0 - 8.0 g/dL; <6.2 - 4.9 mmol/L; <100 - 80g/L	Hemoglobin (Hgb) <8.0 g/dL; <4.9 mmol/L; <80 g/L; transfusion indicated	Life-threatening consequences; urgent intervention indicated	Clinical signs and symptoms are not taken into consideration for grading.
Leukocytosis	-	-	>100,000/mm ³ ; >100 x 10 ⁹ /L	Clinical manifestations of leucostasis; urgent intervention indicated	Clinical signs and symptoms are not taken into consideration for grading; Added ranges in SI unit (x 10 ⁹ /L)
Investigations					
Activated partial thromboplastin time prolonged	>ULN - 1.5 x ULN	>1.5 - 2.5 x ULN	>2.5 x ULN; bleeding	-	Clinical signs and symptoms are not taken into consideration for grading.
Alanine aminotransferase increased	>ULN - 3.0 x ULN if baseline was normal; 1.5 - 3.0 x baseline if baseline was abnormal	>3.0 - 5.0 x ULN if baseline was normal; >3.0 - 5.0 x baseline if baseline was abnormal	>5.0 - 20.0 x ULN if baseline was normal; >5.0 - 20.0 x baseline if baseline was abnormal	>20.0 x ULN if baseline was normal; >20.0 x baseline if baseline was abnormal	Ranges defined for “abnormal baseline” are applied only if baseline > ULN. If baseline < LLN, then ranges for “normal baseline” are applied.
Alkaline phosphatase increased	>ULN - 2.5 x ULN if baseline was normal; 2.0 - 2.5 x baseline if baseline was abnormal	>2.5 - 5.0 x ULN if baseline was normal; >2.5 - 5.0 x baseline if baseline was abnormal	>5.0 - 20.0 x ULN if baseline was normal; >5.0 - 20.0 x baseline if baseline was abnormal	>20.0 x ULN if baseline was normal; >20.0 x baseline if baseline was abnormal	Ranges defined for “abnormal baseline” are applied only if baseline > ULN. If baseline < LLN, then ranges for “normal baseline” are applied.
Aspartate aminotransferase increased	>ULN - 3.0 x ULN if baseline was normal; 1.5 - 3.0 x baseline if baseline was abnormal	>3.0 - 5.0 x ULN if baseline was normal; >3.0 - 5.0 x baseline if baseline was abnormal	>5.0 - 20.0 x ULN if baseline was normal; >5.0 - 20.0 x baseline if baseline was abnormal	>20.0 x ULN if baseline was normal; >20.0 x baseline if baseline was abnormal	Ranges defined for “abnormal baseline” are applied only if baseline > ULN. If baseline < LLN, then ranges for “normal baseline” are applied.
Blood bilirubin increased	>ULN - 1.5 x ULN if baseline was normal;	>1.5 - 3.0 x ULN if baseline was normal;	>3.0 - 10.0 x ULN if baseline was normal;	>10.0 x ULN if baseline was normal;	Ranges defined for “abnormal baseline” are

CTCAE Term	Grade 1	Grade 2	Grade 3	Grade 4	Janssen implementation notes
	> 1.0 - 1.5 x baseline if baseline was abnormal	>1.5 - 3.0 x baseline if baseline was abnormal	>3.0 - 10.0 x baseline if baseline was abnormal	>10.0 x baseline if baseline was abnormal	applied only if baseline > ULN. If baseline < LLN, then ranges for “normal baseline” are applied.
CD4 lymphocytes decreased	<LLN - 500/mm ³ ; <LLN - 0.5 x 10 ⁹ /L	<500 - 200/mm ³ ; <0.5 - 0.2 x 10 ⁹ /L	<200 - 50/mm ³ ; <0.2 x 0.05 - 10 ⁹ /L	<50/mm ³ ; <0.05 x 10 ⁹ /L	
Cholesterol high	>ULN - 300 mg/dL; >ULN - 7.75 mmol/L	>300 - 400 mg/dL; >7.75 - 10.34 mmol/L	>400 - 500 mg/dL; >10.34 - 12.92 mmol/L	>500 mg/dL; >12.92 mmol/L	
CPK increased	>ULN - 2.5 x ULN	>2.5 x ULN - 5 x ULN	>5 x ULN - 10 x ULN	>10 x ULN	
Creatinine increased	Creatine Kinase >ULN - 1.5 x ULN	Creatine Kinase >1.5 - 3.0 x baseline; >1.5 - 3.0 x ULN	Creatine Kinase >3.0 x baseline; >3.0 - 6.0 x ULN	Creatine Kinase >6.0 x ULN	
Fibrinogen decreased	<1.0 - 0.75 x LLN; if abnormal, <25% decrease from baseline	<0.75 - 0.5 x LLN; if abnormal, 25 - <50% decrease from baseline	<0.5 - 0.25 x LLN; if abnormal, 50 - <75% decrease from baseline	<0.25 x LLN; if abnormal, 75% decrease from baseline; absolute value <50 mg/dL	Ranges defined for “abnormal” are applied only on values < LLN. Grade 0 will be assigned to values > ULN.
GGT increased	>ULN - 2.5 x ULN if baseline was normal; 2.0 - 2.5 x baseline if baseline was abnormal	>2.5 - 5.0 x ULN if baseline was normal; >2.5 - 5.0 x baseline if baseline was abnormal	>5.0 - 20.0 x ULN if baseline was normal; >5.0 - 20.0 x baseline if baseline was abnormal	>20.0 x ULN if baseline was normal; >20.0 x baseline if baseline was abnormal	Ranges defined for “abnormal baseline” are applied only if baseline > ULN. If baseline < LLN, then ranges for “normal baseline” are applied.
Haptoglobin decreased	<LLN	-	-	-	
Hemoglobin increased	Increase in >0 - 2 g/dL; Increase in >0 - 20 g/L	Increase in >2 - 4 g/dL; Increase in >20 - 40 g/L	Increase in >4 g/dL; Increase in >40 g/L	-	The increase indicates the level of increase above normal (above ULN). Applied as, e.g. grade 1 (g/dL): >ULN - ULN+2 g/dL; Added ranges in SI unit (g/L).
INR increased	>1.2 - 1.5; >1 - 1.5 x baseline if on anticoagulation; monitoring only indicated	>1.5 - 2.5; >1.5 - 2.5 x baseline if on anticoagulation; dose adjustment indicated	>2.5; >2.5 x baseline if on anticoagulation; bleeding	-	Concomitant therapy or clinical signs and symptoms are not taken into consideration for grading.

CTCAE Term	Grade 1	Grade 2	Grade 3	Grade 4	Janssen implementation notes
Lipase increased	>ULN - 1.5 x ULN	>1.5 - 2.0 x ULN; >2.0 - 5.0 x ULN and asymptomatic	>2.0 - 5.0 x ULN with signs or symptoms; >5.0 x ULN and asymptomatic	>5.0 x ULN and with signs or symptoms	“Asymptomatic” ranges are not taken into consideration for grading, i.e. worst case grading is applied.
Lymphocyte count decreased	<LLN - 800/mm ³ ; <LLN - 0.8 x 10 ⁹ /L	<800 - 500/mm ³ ; <0.8 - 0.5 x 10 ⁹ /L	<500 - 200/mm ³ ; <0.5 - 0.2 x 10 ⁹ /L	<200/mm ³ ; <0.2 x 10 ⁹ /L	
Lymphocyte count increased	-	>4000/mm ³ - 20,000/mm ³ ; >4 - 20 x 10 ⁹ /L	>20,000/mm ³ ; >20 x 10 ⁹ /L	-	Added ranges in SI unit (x 10 ⁹ /L).
Neutrophil count decreased	<LLN - 1500/mm ³ ; <LLN - 1.5 x 10 ⁹ /L	<1500 - 1000/mm ³ ; <1.5 - 1.0 x 10 ⁹ /L	<1000 - 500/mm ³ ; <1.0 - 0.5 x 10 ⁹ /L	<500/mm ³ ; <0.5 x 10 ⁹ /L	Both Neutrophils and segmented neutrophils are graded using these criteria.
Platelet count decreased	<LLN - 75,000/mm ³ ; <LLN - 75.0 x 10 ⁹ /L	<75,000 - 50,000/mm ³ ; <75.0 - 50.0 x 10 ⁹ /L	<50,000 - 25,000/mm ³ ; <50.0 - 25.0 x 10 ⁹ /L	<25,000/mm ³ ; <25.0 x 10 ⁹ /L	
Serum amylase increased	>ULN - 1.5 x ULN	>1.5 - 2.0 x ULN; >2.0 - 5.0 x ULN and asymptomatic	>2.0 - 5.0 x ULN with signs or symptoms; >5.0 x ULN and asymptomatic	>5.0 x ULN and with signs or symptoms	“Asymptomatic” ranges are not taken into consideration for grading, i.e. worst case grading is applied.
White blood cell decreased	<LLN - 3000/mm ³ ; <LLN - 3.0 x 10 ⁹ /L	<3000 - 2000/mm ³ ; <3.0 - 2.0 x 10 ⁹ /L	<2000 - 1000/mm ³ ; <2.0 - 1.0 x 10 ⁹ /L	<1000/mm ³ ; <1.0 x 10 ⁹ /L	
Metabolism and nutrition disorders					
Acidosis	pH <normal, but >=7.3	-	pH <7.3	Life-threatening consequences	pH <normal is implemented as pH <LLN. Clinical signs and symptoms are not taken into consideration for grading.
Alkalosis	pH >normal, but <=7.5	-	pH >7.5	Life-threatening consequences	pH >normal is implemented as pH >ULN. Clinical signs and symptoms are not taken into consideration for grading.

CTCAE Term	Grade 1	Grade 2	Grade 3	Grade 4	Janssen implementation notes
Hypercalcemia	Corrected serum calcium of >ULN - 11.5 mg/dL; >ULN - 2.9 mmol/L; Ionized calcium >ULN - 1.5 mmol/L	Corrected serum calcium of >11.5 - 12.5 mg/dL; >2.9 - 3.1 mmol/L; Ionized calcium >1.5 - 1.6 mmol/L; symptomatic	Corrected serum calcium of >12.5 - 13.5 mg/dL; >3.1 - 3.4 mmol/L; Ionized calcium >1.6 - 1.8 mmol/L; hospitalization indicated	Corrected serum calcium of >13.5 mg/dL; >3.4 mmol/L; Ionized calcium >1.8 mmol/L; life-threatening consequences	Clinical signs and symptoms are not taken into consideration for grading.
Hyperkalemia	Potassium >ULN - 5.5 mmol/L	Potassium >5.5 - 6.0 mmol/L; intervention initiated	Potassium >6.0 - 7.0 mmol/L; hospitalization indicated	Potassium >7.0 mmol/L; life-threatening consequences	Clinical signs and symptoms are not taken into consideration for grading.
Hypermagnesemia	Magnesium >ULN - 3.0 mg/dL; >ULN - 1.23 mmol/L	-	Magnesium >3.0 - 8.0 mg/dL; >1.23 - 3.30 mmol/L	Magnesium >8.0 mg/dL; >3.30 mmol/L; life-threatening consequences	Clinical signs and symptoms are not taken into consideration for grading.
Hypernatremia	Sodium >ULN - 150 mmol/L	Sodium >150 - 155 mmol/L; intervention initiated	Sodium >155 - 160 mmol/L; hospitalization indicated	Sodium >160 mmol/L; life-threatening consequences	Clinical signs and symptoms are not taken into consideration for grading.
Hypertriglyceridemia	Triglycerides 150 mg/dL - 300 mg/dL; 1.71 mmol/L - 3.42 mmol/L	Triglycerides >300 mg/dL - 500 mg/dL; >3.42 mmol/L - 5.7 mmol/L	Triglycerides >500 mg/dL - 1000 mg/dL; >5.7 mmol/L - 11.4 mmol/L	Triglycerides >1000 mg/dL; >11.4 mmol/L; life-threatening consequences	Clinical signs and symptoms are not taken into consideration for grading.
Hypoalbuminemia	Albumin <LLN - 3 g/dL; <LLN - 30 g/L	Albumin <3 - 2 g/dL; <30 - 20 g/L	Albumin <2 g/dL; <20 g/L	Life-threatening consequences; urgent intervention indicated	Clinical signs and symptoms are not taken into consideration for grading.
Hypocalcemia	Corrected serum calcium of <LLN - 8.0 mg/dL; <LLN - 2.0 mmol/L; Ionized calcium <LLN - 1.0 mmol/L	Corrected serum calcium of <8.0 - 7.0 mg/dL; <2.0 - 1.75 mmol/L; Ionized calcium <1.0 - 0.9 mmol/L;	Corrected serum calcium of <7.0 - 6.0 mg/dL; <1.75 - 1.5 mmol/L; Ionized calcium <0.9 - 0.8 mmol/L;	Corrected serum calcium of <6.0 mg/dL; <1.5 mmol/L; Ionized calcium <0.8 mmol/L;	Clinical signs and symptoms are not taken into consideration for grading.

CTCAE Term	Grade 1	Grade 2	Grade 3	Grade 4	Janssen implementation notes
		symptomatic	hospitalization indicated	life-threatening consequences	
Hypoglycemia	Glucose <LLN - 55 mg/dL; <LLN - 3.0 mmol/L	Glucose <55 - 40 mg/dL; <3.0 - 2.2 mmol/L	Glucose <40 - 30 mg/dL; <2.2 - 1.7 mmol/L	Glucose <30 mg/dL; <1.7 mmol/L; life-threatening consequences; seizures	Clinical signs and symptoms are not taken into consideration for grading. Urine glucose is not graded.
Hypokalemia	Potassium <LLN - 3.0 mmol/L	Symptomatic with Potassium <LLN - 3.0 mmol/L; intervention indicated	Potassium <3.0 - 2.5 mmol/L; hospitalization indicated	Potassium <2.5 mmol/L; life-threatening consequences	“Symptomatic” ranges are applied for grade 2, grade 1 not assigned, i.e. worst case applied. Clinical signs and symptoms are not taken into consideration for grading of grade 3 and 4.
Hypomagnesemia	Magnesium <LLN - 1.2 mg/dL; <LLN - 0.5 mmol/L	Magnesium <1.2 - 0.9 mg/dL; <0.5 - 0.4 mmol/L	Magnesium <0.9 - 0.7 mg/dL; <0.4 - 0.3 mmol/L	Magnesium <0.7 mg/dL; <0.3 mmol/L; life-threatening consequences	Clinical signs and symptoms are not taken into consideration for grading.
Hyponatremia	Sodium <LLN - 130 mmol/L	Sodium 125-129 mmol/L and asymptomatic	Sodium 125-129 mmol/L symptomatic; 120-124 mmol/L regardless of symptoms Sodium <130-120 mmol/L	Sodium <120 mmol/L; life-threatening consequences	Clinical signs and symptoms are not taken into consideration for grading. Worst case (“<130-120 mmol/L” for grade 3 added by Janssen) is applied across grade 2/3 ranges: 120-129 mol/L assigned to grade 3, grade 2 not used.
Renal and urinary disorders					
Proteinuria	1+ proteinuria; urinary protein \geq ULN - <1.0 g/24 hrs; urinary protein \geq ULN - <1000 mg/day	Adult: 2+ and 3+ proteinuria; urinary protein 1.0 - <3.5 g/24 hrs;	Adult: 4+ proteinuria; urinary protein \geq =3.5 g/24 hrs;	-	In case both 24-h urine collection and dipstick are collected, then worst case is taken, as opposed to having 24-h urine

CTCAE Term	Grade 1	Grade 2	Grade 3	Grade 4	Janssen implementation notes
		
urinary protein 1000 - <3500 mg/day
 
Pediatric: Urine P/C (Protein/Creatinine) ratio 0.5 - 1.9; Urine P/C (Protein/Creatinine) 56.5 – 214.7 g/mol
	
urinary protein >=3500 mg/day;
 
Pediatric: Urine P/C (Protein/Creatinine) ratio >1.9; Urine P/C (Protein/Creatinine) >214.7 g/mol
		
collection take precedence over dipstick. Added ranges in SI unit for urinary protein (mg/day) and for urine P/C (g/mol). Pediatric grading is applied to age range [0-18]. Adult grading is applied for ages [>18].

* Grade 0 is assigned to a lab assessment when the lab test is described in the table, but the lab value is not assigned a grade 1 or higher.

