10.2. Appendix 2: Clinical Laboratory Tests

The following tests will be performed according to the Schedule of Activities (Section 1.3) by the central laboratory:

Protocol-Required Laboratory Assessments

Laboratory Assessments	Parameters		
Hematology	Platelet count Red blood cell count Hemoglobin Hematocrit	RBC Indices: MCV MCH	White Blood Cell count with Differential: Neutrophils Lymphocytes Monocytes Eosinophils Basophils Bands
Clinical Chemistry	Sodium Potassium Chloride Bicarbonate BUN Creatinine Glucose Aspartate aminotransferase (AST)/Serum glutamic-oxaloacetic Alanine aminotransferase (ALT)/Serum glutamic-pyruvic	Total bilirubin Indirect bilirubin Alkaline phosphatase Calcium Phosphate Albumin Total protein Lactic acid dehydrogenase (LDH)	
	Note: Details of liver chemistry stopping criteria and required actions and follow-up are given in Section 10.7, Appendix 7: Liver Safety: Suggested Actions and Follow-Up Assessments		
Other Laboratory Tests	
 • Serum (or additional Urine) Pregnancy Testing for women of childbearing potential only • Lipid panel: HDL, LDL (calculated), Total cholesterol, triglycerides (Weeks 0 and 16) • Serology (HIV antibody, HBsAg, hepatitis B surface antibody [anti-HBs], hepatitis B core antibody [anti-HBc], and hepatitis C virus antibody) • QuantiFERON-TB® test 		

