5.6.3. Clinical Laboratory Tests

The clinical laboratory parameters to be evaluated by the central laboratory include but are not limited to:

- **Hematology** will include but are not limited to the following: Basophils, Eosinophils, Hemoglobin, Lymphocytes, Monocytes, Neutrophils, Platelets, WBC, CRP and ESR.
- **Chemistry** will include but are not limited to the following: ALT, AST, Albumin, Alkaline Phosphatase, Bicarbonate (CO₂), Calcium, Chloride, Creatinine, GGT, Glucose, Potassium, SGOT, SGPT, Sodium, Total Bilirubin, Total Protein, Urea Nitrogen.

Participants in the safety analysis set with toxicity grades ≥ 2 will be listed.

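### SAP Appendix 10 names creatine kinase in every grade cell of the *Creatinine increased* row, so serum creatinine has no explicit grading rule

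*SAP*

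**What the plan says.** SAP 6.10 sets out how laboratory values are graded, opening with "The grading scale use for lab assessments is based on" CTCAE; no version is given. Each row has a CTCAE term, four grade cells and a column for the sponsor's implementation notes.

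The row with the term *Creatinine increased* has creatine kinase as the analyte in each of its four grade cells. Its Grade 2 cell is "Creatine Kinase >1.5 - 3.0 x baseline; >1.5 - 3.0 x ULN", and its notes cell is blank. The row directly above, *CPK increased*, gives Grade 2 as ">2.5 x ULN - 5 x ULN".

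The table footnote says that "Grade 0 is assigned to a lab assessment when the lab test is described in the table" and the value does not reach Grade 1 or higher.

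SAP 5.6.3 includes serum creatinine in the chemistry list ("Calcium, Chloride, Creatinine, GGT, Glucose") and states the output: "Participants in the safety analysis set with toxicity grades" of 2 or more are to be listed. Protocol Appendix 2 (section 10.2) also has creatinine in the chemistry panel ("Bicarbonate BUN Creatinine Glucose").

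**The concern.** A grading table has to tell the programmer which analyte each set of cut-offs applies to. Here the label gives one analyte and all four cells give another, and no note resolves the conflict.

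The Grade 2 or higher listing is the only laboratory output the SAP specifies after early termination. Protocol 9.4.4 had also planned descriptive laboratory statistics, and these are no longer provided. Clinically significant laboratory abnormalities remain among the secondary safety endpoints in SAP 1.1. If the cells were applied as written, no creatinine elevation could appear in the listing, and its absence could be mistaken for a clean renal result.

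**Working it through.** The plan gives no figure to reproduce. The check compares rows and counts them.

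**1. The row against its neighbour.** Upper-limit-of-normal (ULN) cut-offs from Appendix 10, leaving aside the baseline multiples in Grades 2 and 3 of the creatinine row:

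| Row | Analyte in cells | Grade 1 | Grade 2 | Grade 3 | Grade 4 |
|---|---|---|---|---|---|
| *CPK increased* | none (label only) | >1 to 2.5 | >2.5 to 5 | >5 to 10 | >10 |
| *Creatinine increased* | creatine kinase, 4 of 4 | >1 to 1.5 | >1.5 to 3.0 | >3.0 to 6.0 | >6.0 |

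**2. Literal reading, effect on creatine kinase.** It would have two scales at once:

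| Multiple of ULN | Grade by CPK row | Grade by creatinine row |
|---|---|---|
| >1 to 1.5 | 1 | 1 |
| >1.5 to 2.5 | 1 | 2 |
| >2.5 to 3 | 2 | 2 |
| >3 to 5 | 2 | 3 |
| >5 to 6 | 3 | 3 |
| >6 to 10 | 3 | 4 |
| >10 | 4 | 4 |

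The rows disagree in three bands. The first, >1.5 to 2.5 x ULN, decides whether a participant enters the Grade 2 or higher listing.

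**3. Literal reading, effect on serum creatinine.** I looked for any other row that could grade it.

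- Blood and lymphatic: 2 rows. Investigations: 21. Metabolism and nutrition: 13. Renal and urinary: 1. Total 2 + 21 + 13 + 1 = 37.
- Rows labelled for serum creatinine: 1, the row in question.
- Other mentions of creatinine: one, in the pediatric part of the proteinuria row ("Urine P/C (Protein/Creatinine) ratio 0.5 - 1.9"). This is a urine ratio, not a serum criterion.

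Serum creatinine therefore has no stated cut-off. By the footnote it is Grade 0 if the label counts as describing the test, and ungraded if it does not. Neither can reach Grade 2.

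**4. Label reading.** The four ranges apply to serum creatinine. A value above 3.0 and up to 6.0 x ULN, for instance, is Grade 3 and is listed; on the literal reading the same value is not listed.

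**5. Which reading the text favours.** Of the 21 Investigations rows, 20 leave the analyte to the label, and only this one names an analyte in its cells. Serum creatinine is in both routine chemistry lists. Creatine kinase is named in neither, although the SAP list is not exhaustive; the protocol asks for it only in liver-event follow-up (Appendix 7). The label is the more plausible guide, but the SAP does not say so.

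**6. Could it be an extraction fault?** Unlikely. The same name stands in four separate cells, each with a complete range, and the CPK row above is intact.

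**The case against.** The strongest reply is that the intent is plain. Grading is keyed on the CTCAE term, which says creatinine. A second creatine kinase scale below the CPK row would make the table contradict itself, and where the sponsor departs from a standard range the notes column generally says so. On this view it is a drafting slip, and the harm depends on a programmer ignoring the row's own term. That stands as an argument about likelihood. It does not make the text correct: an operative rule should not leave the analyte to inference, and the program is not in the documents.

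The consequences are also small. The trial stopped early with few participants, and no formal analyses are planned. Investigators must record clinically relevant laboratory changes as adverse events (Protocol 8.2.4), and treatment-emergent events are listed (SAP 5.6.2). The SAP introduction also promises safety listings in general. All of this stands and sets the severity. The adverse event route depends on the investigator's judgement of relevance, whereas the graded listing applies a fixed rule, so the first does not fully replace the second.

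Finally, the missing CTCAE version affects all 37 rows and is not evidence of this error. That is right. It matters here only because, without it, the documents alone cannot confirm that the cut-offs in this row belong to creatinine.

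**Conclusion.** The row is wrong as written: 4 of 4 grade cells name creatine kinase and none names creatinine. Taken literally, it gives creatine kinase two conflicting scales and leaves a routine chemistry test with no route into the only specified laboratory listing. Taken by its label, it misses no value that meets its cut-offs.

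The severity is minor. The loss is conditional on the literal reading having been programmed, which the documents neither show nor exclude. How many participants would be affected cannot be derived from them. This is not a demonstrated gap in renal safety reporting.

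**What to change.** In SAP Appendix 10, replace creatine kinase with serum creatinine in the four grade cells of *Creatinine increased*, and keep creatine kinase only under *CPK increased*. Check that the grading lookup maps the row to serum creatinine. If it does not, correct it and rerun the Grade 2 or higher listing if that has already been produced.

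As a secondary step, state the CTCAE version and confirm this row's thresholds against it.

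The cost is one row of SAP text, one version statement and one lookup check, with a rerun of a single listing only if the check fails.
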